1. PROGRAM SUMMARY

Please provide a brief summary of your grant project including the needs to be addressed, the services provided, and the population served.

The Strong Fathers, Stronger Families-Midsouth (SFSF-Midsouth) FIRE Project conducted by the Structured Employment Economic Development Corporation (Seedco) builds upon Seedco's regional capacity and track record accumulated since 2004 and adapts ten years of experience operating an ACF-funded Responsible Fatherhood Program in New York City to meet the needs of fathers in the Memphis, TN metropolitan region.

Sustained long term employment of parents is one of the key driving factors affecting child well-being. Fatherhood programs may not have the lasting effects program planners and policy makers expect to see, as participants who have successfully completed a program and started a job often do not maintain employment. This inability to sustain employment has a ripple effect across other components of fatherhood, including parenting or partnership relationships.

Needs: Seedco's targeted geographic community for the proposed SFSF-Midsouth program is Shelby County and Tipton County in Tennessee and Crittenden County in Arkansas (the Greater Memphis Metropolitan region). This region is distinguished by high rates of poverty, concentrations of African American populations, and a largely urban center surrounding the Greater Memphis Metropolitan area. These communities are among the poorest in the region, with resources and opportunities further constrained by racial disparity. Participants served via this funding face a challenging economic climate and many face societal and emotional barriers. Seedco's needs analysis confirmed what the agency already knows from its experience serving many fathers, families, and local residents— that these individuals grapple with poverty, incarceration, crime, and single parenthood, or family instability. In short, this region needs and deserves a quality HMRF program.

Services: The SFSF-Midsouth Program will provide economic stability, healthy relationship, and parenting/fatherhood education via evidence-based curricula in combination with intensive case management to participants based on the results of a needs assessment completed at program enrollment.

Population: The SFSF-Midsouth Program proposes to serve low-income fathers who face barriers to engagement with their children. These participants will be primarily young fathers, including biological, expectant, and adoptive fathers, stepfathers, and acknowledged father figures. Recruitment will focus on at-risk young fathers, low-income fathers, and active-duty military and veteran fathers living in Shelby County, TN, Tipton County, TN, and Crittenden County, AR. Specific numbers to be served are in the chart below:

PROGRAM PARTICIPATION TARGETS

Milestone	Year 1 4/1/21- 9/29/21	Year 2 9/30/21- 9/29/22	Year 3 9/30/22- 9/29/23	Year 4 9/30/23- 9/29/24	Year 5 9/30/24- 9/29/25	Total
Individuals Screened	225	450	450	450	450	2,025
Participants Enrolled	175	350	350	350	350	1,575
Participants who attend at least one primary workshop	175	350	350	350	350	1,575

Participants who attend at least 50% of primary workshops	165	330	330	330	330	1,485
Participants Graduating Healthy Relationship & Parenting Curricula (attend at least 90% of primary workshops)	158 (90%)	315 (90%)	315 (90%)	315 (90%)	315 (90%)	1,418
Participants who attend 100% of primary workshops	118	236	236	236	236	1062
Participants Placed in Jobs	105(60%)	210 (60%)	210 (60%)	210 (60%)	210 (60%)	945
Job Retention- 30 days	87 (50%)	175 (50%)	175 (50%)	175 (50%)	175 (50%)	787
Job Retention- 60 days	70 (40%)	140 (40%)	140 (40%)	140 (40%)	140 (40%)	630
Job Retention- 90 days	50	100	100	100	100	450
Job Retention- 180 days	40	80	80	80	80	360
Return Post-Graduation for Long-Term Case Management	87	175	175	175	175	787

Memorandum of changes to the Evaluation Study.

- SEEDCO Midsouth will aim to serve the same number of individuals in the descriptive study as in the RCT with a different estimated minimum effect size for the descriptive study. (Evaluation enrollment targets remain unchanged)
- The one-year local evaluation follow-up survey will no longer be collected and has been removed from the evaluation plan.
- The previously administered OLLE pre- and post-surveys will not be administered, as the measures needed to answer R1, R2, and R3 come from nFORM.

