Dosage will be measured by percent of target primary workshops participants attend on average (using 90% as a benchmark), and categories of attendance (initial, halfway, 90%, 100%) will be reported and compared to targets established by the program and reported on page 3 above. Exploratory analysis will examine how dosage varies by workshop characteristics (e.g., timing and length of sessions) and participant characteristics (e.g., age, employment status, relationship status)?

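### The 1,575 enrolment target counts a full Year 5, but enrolment closes on 3/31/2025; at the table's own pace the window yields about 1,400

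*Protocol*

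**What the plan says.** The participation table in Protocol Section 1 (Program Summary) runs from "Year 1 4/1/21- 9/29/21" to "Year 5 9/30/24- 9/29/25". The enrolment row reads "Participants Enrolled 175 350 350 350 350 1,575". The attendance rows are on the same basis: "Participants who attend at least 50% of primary workshops 165 330 330 330 330 1,485", then "158 (90%) 315 (90%) 315 (90%) 315 (90%) 315 (90%) 1,418" for those attending at least 90% of workshops, then "Participants who attend 100% of primary workshops 118 236 236 236 236 1062". The memorandum below the table says of the move to a descriptive study: "Evaluation enrollment targets remain unchanged".

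Protocol Section 3 (Evaluation Enrollment) gives 4/1/2021 to 3/31/2025 for program enrolment and for study enrolment, in both the implementation and the descriptive evaluation. Protocol Section 4 (Evaluation Timeline) ends pre- and post-survey collection on 3/31/2025 as well. Evaluation Plan Section 9.2 places the exit survey about 8 weeks after enrolment.

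The SAP (Analytic approach, dosage) measures average dosage against a 90% benchmark. It adds that categories of attendance will be "compared to targets established by the program and reported on page 3 above". It does not say whether that comparison uses counts or shares. The dosage hypothesis in Evaluation Plan Section 4 is a percentage of enrollees.

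**The concern.** The enrolment total and the enrolment window do not describe the same period. The table counts twelve months of enrolment in Year 5, while Section 3 allows about six. Because Section 3 closes program enrolment too, fathers who join the program later in Year 5 cannot make up the difference.

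Two things depend on this. First, Section 3 makes program enrolment one of the matters the implementation evaluation is to judge. Measured against 1,575, a program that kept exactly to its planned pace would appear to have under-recruited. Second, the SAP refers back to this table for the attendance categories. If total counts are used, the same gap carries into every category, and a reader could take a calendar mismatch for poor attendance.

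**Working it through.** **Inputs.** Yearly targets and year dates come from the table in Protocol Section 1, the enrolment end date from Section 3, the survey end date from Section 4, and the 8-week lag from Evaluation Plan Section 9.2.

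**1. Reproduce the plan's totals** (Year 1 + 4 × the later-year figure).
- Enrolled: 175 + 4 × 350 = 1,575
- At least 50% of workshops: 165 + 4 × 330 = 1,485
- At least 90%: 158 + 4 × 315 = 1,418
- 100%: 118 + 4 × 236 = 1,062

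All four agree with the table, so its addition is sound.

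**2. Open days.** Year 1 has 182 days. Year 5 has 365 days, of which 9/30/2024 to 3/31/2025 inclusive is 183. The open share of Year 5 is 183/365 = 0.501.

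**3. Planned pace.** Year 1: 175/182 = 0.96 per day. Years 2 to 4: 350/365 = 0.96 per day. The half-length Year 1 was given half the annual target. Year 5 has about the same number of open days but carries the full 350.

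**4. Enrolment in the stated window at that pace.** 175 + 3 × 350 + 350 × 183/365 = 175 + 1,050 + 175.5 = 1,400.5. The shortfall is 1,575 − 1,400.5 = 174.5, and 174.5/1,575 = 11.1%.

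**5. Pace needed for 1,575.** 350/183 = 1.91 per day in Year 5, which is 1.99 times the earlier pace. Spread over the whole window of 1,461 days, it is 1,575/1,461 × 365 = 393 per year, or 1.12 times 350.

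**6. Range.** 1,225 with no Year 5 enrolment (175 + 1,050), about 1,400 at a steady pace, and 1,575 if all 350 are enrolled by 3/31/2025.

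**7. Attendance rows, pro-rated in the same way.**

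| Row | Table total | At planned pace to 3/31/2025 | Share of enrolled, either way |
|---|---|---|---|
| At least 50% | 1,485 | 165 + 990 + 165.5 = about 1,320 | 94.3% |
| At least 90% | 1,418 | 158 + 945 + 157.9 = about 1,261 | 90.0% |
| 100% | 1,062 | 118 + 708 + 118.3 = about 944 | 67.4% |

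Each count falls by 11.1%. The shares do not move, because numerator and denominator shrink together.

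**8. Survey window.** Eight weeks before 3/31/2025 is 2/3/2025. Fathers enrolled after about that date could not have both surveys inside the window: 350 × 56/365 = 53.7, about 54 at the planned pace. If 350 were enrolled evenly over the 183 days, the number would be 350 × 56/183 = about 107.

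**The case against.** A reader might infer that the plan can deliver only about 1,400 fathers and that the attendance comparison must fail by construction. The documents do not support that. The table gives yearly totals with no schedule within the year, so even accrual in Year 5 is an inference, though the half-size Year 1 target supports it. The 350 may be meant for the first six months. That would be demanding but not impossible.

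Nor does the SAP commit to counts. Its average-dosage benchmark and the dosage hypothesis are percentages, and the graduation row prints 90% beside each yearly count. On the other side, the 50% and 100% attendance rows carry counts only, so a count comparison is a natural reading of the reference to the table. Even then, comparisons by year would be unaffected for Years 1 to 4. The text leaves the basis open.

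A reader might also take 1,575 as the study's sample size and call it overstated. The table sets program participation targets. The SAP defines the study sample as consenting fathers with both surveys and puts its anticipated size in an Appendix B diagram that is not in the text available here. The memorandum's reference to unchanged evaluation targets gives no number. For the same reason, subtracting the 54 late enrollees from 1,400 would not give an evaluation sample size, since it ignores non-consent and dropout.

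Finally, a Year 5 column ending on 9/29/2025 is not itself an error. The table also holds job-retention milestones up to 180 days, and 9/29/2025 falls 182 days after 3/31/2025. That explains the column's end date but not a full-year figure in the enrolment row.

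**Conclusion.** The mismatch stands. The total of 1,575 assumes a full Year 5 of enrolment, and the stated window covers 183 of its 365 days. At the table's own constant pace the window yields about 1,400, or 11% fewer. This rests on even accrual within Year 5, which the table's pattern suggests but no text states.

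The effect on conclusions is conditional. Enrolment judged against 1,575, or attendance judged on total counts, would show an 11% shortfall with performance exactly on plan. Attendance judged as shares would show none. The effect on the paired t-tests is small: if the study sample shrank in proportion to enrolment, the detectable effect would grow by a factor of √(1,575/1,400) = 1.06. No outcome or test changes.

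The survey dates are a related gap. Under the stated dates, fathers enrolled in the last 8 weeks cannot qualify for the study sample.

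**What to change.** 1. In Protocol Section 1, reconcile the Year 5 target with the 3/31/2025 end date. Either restate the total as about 1,400 for 4/1/2021 to 3/31/2025, with the attendance rows on the same basis, or state that all 350 are to be enrolled by that date.
2. In the SAP's dosage paragraph, say that attendance categories are compared as shares of enrolled fathers (94%, 90% and 67%) rather than as counts.
3. Reconcile the survey collection end date in Protocol Section 4 with the lag of about 8 weeks to the exit survey. Either let exit surveys run on after enrolment closes, or state that fathers enrolled after about 2/3/2025 will not be in the study sample.

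Items 1 and 2 cost wording only; if the total is restated, it becomes about 11% smaller. Item 3 is also wording if the late enrollees are excluded. Extending collection would add about 8 weeks of exit surveys.

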2. EVALUATION GOALS

Please briefly describe key goals of your evaluation and what you hope to learn below.

The goals of the evaluation activities are to 1) Support the effective implementation of the SFSF- Midsouth FIRE Program with a rigorous Implementation Evaluation and a high-quality Continuous Quality Improvement (CQI) process, and 2) to conduct a rigorous Descriptive Study evaluation that answers the key research questions. The research questions seek to understand if participants report significantly better parenting relationship behaviors, coparenting behaviors, and economic stability outcomes after program participation.

3. EVALUATION ENROLLMENT

Please provide the expected start and end dates for program and evaluation enrollment using the tables below. For impact studies, please indicate expected start and end dates for each study group.

IMPLEMENTATION EVALUATION Please leave blank if not conducting an implementation study.			
	Program Enrollment	Study Enrollment	
Start Date	4/1/2021	4/1/2021	
End Date	3/31/2025	3/31/2025	
Definition	Evaluating the extent to which the program is being implemented as intended, including program enrollment and retention outcomes.	Evaluating the extent to which the evaluation is being implemented as intended, including study enrollment, consent, and survey response rates.	

DESCRIPTIVE EVALUATION Please leave blank if not conducting a descriptive outcome evaluation.			
Program Enrollment Study Enrollment			
Start Date	4/1/2021	4/1/2021	
End Date	3/31/2025	3/31/2025	
Definition	All participants across all grant years with no pilot program	All participants across all grant years with no pilot program	

4. EVALUATION TIMELINE

Please include a timeline for key activities of the evaluation below. Example of activities may include IRB submission, staff training, waves of data collection, analysis period, and report writing and submission.

Evaluation Activity	Start Date	End Date
Data collection (pre- and post-surveys) Note: Prior to April 2021, SEEDCO was aiming to conduct an impact evaluation. Data collected during this time will still be used for the descriptive evaluation.	4/1/2021	3/31/2025
Development and submission of Descriptive Evaluation Plan document	6/1/2023	7/30/2023
IRB Amendment Approval of descriptive study activity changes	7/24/2023	7/28/2023

Note: The original impact study, including a descriptive pilot period before randomization, was approved by the IRB in 2021 and was renewed annually in 2022 and 2023. The IRB approval indicated here is for an amendment describing the changes in study activities.		
Study Registration	7/28/2023	7/31/2023

^{*} you may add rows by hitting the tab button, or right click and select insert row below

EVALUATION PLAN

1. RESEARCH QUESTIONS

1.1. OVERVIEW OF RESEARCH QUESTIONS

The primary overall research questions for this descriptive evaluation, which will be assessed utilizing pre- and post-surveys from nFORM, focus on program services and seeks to understand, "Is Strong Fathers, Stronger Families program participation associated with better participant outcomes?" This overall line of inquiry is operationalized by focusing on specific short-term outcomes to determine if parenting, co-parenting, and economic stability outcomes are improved after program participation.

No	Research Question	Implementation or Outcome?
11	Are participants offered primary workshops and support services as intended (fidelity)?	Implementation
12	How many primary workshops do participants attend (dosage), and how does this vary by workshop characteristics (e.g., timing and length of sessions) and participant characteristics (e.g., age, employment status, relationship status)?	Implementation
R1	Do SFSF-Midsouth participants experience significant increases in Co-parenting Relationship outcomes after program participation?	Primary Outcome
R2	Do SFSF-Midsouth participants experience significant increases in Parenting Relationship outcomes after program participation?	Primary Outcome
R3	Do SFSF-Midsouth participants experience significant increases in economic stability outcomes after program participation?	Primary Outcome

1.2. OUTCOME RESEARCH QUESTIONS

For each outcome research question listed above, whether a descriptive or impact design, summarize the inputs (e.g., program components, program supports, implementation features, etc.), target population (e.g., the population for which the effect will be estimated) and the outcomes (e.g., child well-being, father-child engagement, etc.) that will be examined to answer the research question(s). Comparisons for descriptive evaluations may reflect circumstances before the grant, pre-treatment, or pre-determined benchmark from other studies with similar interventions.

Research Question Number Should correspond to the number indicated in Table 1.1 above	Intervention Program component or set of activities that the evaluation will test or examine	Target Population Population for which the effect of the treatment will be estimated	Comparison What the intervention will be compared to (e.g., pre-intervention for descriptive designs)	Outcome Changes that are expected to occur as a result of the intervention	Confirmatory or Exploratory? Confirmatory: those upon which conclusions will be drawn Exploratory: those that may provide additional suggestive evidence
R1	SFSF primary workshop curricula (40 hours)	Low-income, minority, young fathers (and father figures) in the Greater Memphis area	Pre- intervention	Improved co- parent relationships	Confirmatory
R2	SFSF primary workshop curricula (40 hours)	Low-income, minority, young fathers (and father figures) in the Greater Memphis area	Pre- intervention	Improved parenting relationships	Confirmatory
R3	SFSF primary workshop curricula	Low-income, minority, young fathers (and father figures) in the Greater Memphis area	Pre- intervention	Improved economic stability	Confirmatory

^{*} you may add rows by hitting the tab button, or right click and select insert row below

2. BACKGROUND

For each outcome research question listed in 1.1, whether descriptive or impact design, briefly summarize the previous literature or existing research that informs the stated research question and how the evaluation will expand the evidence base. Explain why the research questions are of specific interest to the program and/or community. Only a short summary paragraph description is needed below. Additional documentation, such as a literature review, may be appended to this document.

Research Question	Existing Research	Contribution to the Evidence Base	Interest to the Program and/or Community
R1	Research with fathers in fatherhood programs has shown that co-parenting is a multidimensional construct with both positive and negative components, often made more challenging by the presence of new intimate relationships for co-parents. At the same time co-parenting programming has been shown to impact attitudes and beliefs about co-parents. One of the major areas of tension between co-parents is often financial support of the child.	This study has the potential to show how employment support services, combined with fatherhood programming, affects participant co-parenting relationships	Seedco has a strong interest in learning how to best provide services to fathers that improve co-parenting relationships.
R2	The research on father -child relationships in low-income and fragile families is limited and few have examined the impact when fathers live separately from their child and were not married at the time of birth. It has been shown that couple-oriented programs, such as those provided in fatherhood programs, can have an impact on father involvement.	This study has the potential to show how employment support services, combined with fatherhood programming, affects participant parenting relationships.	Seedco has a strong interest in learning how to best provide services to fathers that improve parenting relationships.
R3	Previous research has explored the potential impact of combining employment support services with fatherhood programming on participant economic stability. These services have been shown to help fathers acquire new skills, improve their resumes, and navigate the job market	This study has the potential to show how employment support services, combined with fatherhood programming, affects participant economic stability.	By addressing both employment and fatherhood-related challenges simultaneously, these integrated programs can offer comprehensive support and foster positive outcomes. Fathers participating in such programs are more likely to find stable employment,

effectively. By increasing their employment opportunities, participants can secure stable jobs with better wages, benefits, and long-term prospects. experience increased job satisfaction, and have higher earning potential. This, in turn, contributes to their economic stability* and the overall well-being of their families and communities.

*Data on financial well-being and economic stability is collected via surveys administered to the participants. The Applicant Characteristics Survey (ACS) survey asks questions on employment status. Additionally, the enrollment tab on nFORM displays information on primary reasons for enrollment including to find a job. Similarly, in the client outcome tab, participants can be filtered based on varied employment status. nFORM Entrance and Exit survey also collect information on economic stability. These measures provide a sound understanding of the participant's rationale for joining the program as well as measuring how effective the program has been to improve participant's economic stability.

3. LOGIC MODEL

Clearly demonstrate how the research question(s) (and the related implementation features and/or participant outcomes) link to the proposed logic model and the theory of change for the program. You may append a copy of your logic model to this document.

See Appendix A for Theory of Change Logic Model

The appended logic model specifies a theory of change for delivering fatherhood curriculum and postemployment services to SFSF participants. Service delivery processes specified in the model are linked to the desired outcome. Model specification incorporates a descriptive study design to determine if participants report significantly improved primary outcomes after program participation.

Service delivery processes: Key aspects of service delivery processes in the theory of change—goals, inputs, activities, and outputs—articulate the experiences that are designed to solve specific problems for those who agree to participate in the SFSF Program. Solving each problem identifies three broad service delivery goals to maximize participation benefits for study groups as explained below:

- Goal 1 Deliver primary workshop hours and support services: Program participants will receive the Blueprint and 24/7 Dad curricula, in combination with employment support services and case management through Seedco, but only after receiving an orientation about the SFSF and giving project staff informed consent to participate in study activities.
- Goal 2 Conduct Continuous Quality Improvement (CQI) to ensure full implementation of program: Reports prepared and presented to the CQI Team by evaluators will use a series of performance indicators to track key outputs over time to identify any primary or support SFSF services delivered to program participants that might fall short of the intended amounts to be offered (i.e., fidelity standards) and received (i.e., dosage thresholds) by them. The CQI Team will then work with project staff to develop and implement performance interventions to address any outputs that need improvement to ensure the services offered to and received by participants meet the intended amounts by the end of each program year.
- Desired Outcomes: Outcomes specified in the logic model theorize the primary outcomes that are
 desired for program participants after they receive primary workshop hours, case management support
 services, and employment support services.

^{*} you may add rows by hitting the tab button, or right click and select insert row below

